At the randomization visit (day 1), patients will be randomly assigned to 1 of 2 treatment groups of 225 mg sc fremanezumab or placebo in a 1:1 ratio. Patients will receive their assigned study treatment on visit 2 (day 1), visit 3 (day 29), and visit 4 (day 57) and then continue into the open-label extension phase in which all patients will receive a quarterly dose of 675 mg sc fremanezumab on visit 5 (day 85). Investigators can contact patients in between study visits per their clinical judgment.

Patients who complete all scheduled visits will have procedures and assessments performed at visit 6 (end of treatment [EOT]). Patients who withdraw from the study before completing the 24-week treatment phase will have visit 6 (EOT) procedures and assessments performed at their final visit. The end of study is defined as the last visit (end-of-treatment/early withdrawal visit [visit 6]) of the last patient.

Study procedures and assessments with their timing are summarized in Table 4 of the study protocol.

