## **2.4. Sample Size and Power Considerations**

A sample size of 288 (144 per treatment group) evaluable patients completing the study will provide 90% power to detect a treatment difference of 2 days with a common standard deviation of 5.2 days in changes from the 28-day baseline period in monthly average migraine days between active and placebo groups at a 2-sided alpha level of 0.05. This sample size will provide approximately 80% power to detect a treatment difference of 2 points with a common standard deviation of 6 points in the change from randomization visit (day 1) in HAM-D 17 total score at a 2-sided alpha level of 0.05. Assuming a 15% drop-out rate, approximately 340 patients (approximately 170 patients per treatment group) will be randomized.

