### **2.5.2. Final Analyses and Reporting**

All analyses identified in this SAP will be performed after the final database lock.

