### 6.2.2. Primary Efficacy Analysis

The hypothesis testing for the primary analysis is:

$$H_o : \delta_1 = \delta_2 \quad vs \quad H_a : \delta_1 \neq \delta_2$$

where  $\delta_1$  and  $\delta_2$  are the mean change from baseline in the monthly average number of migraine days for the fremanezumab treatment group and the placebo treatment group respectively.

The primary efficacy endpoint will be analyzed using an analysis of covariance (ANCOVA) model with sex, region (United States, European, or rest of world), migraine classification (ie, CM or EM), baseline PHQ-9 score category (10 to 14, 15 to 19, and  $\geq 20$ ), and treatment as factors and baseline number of migraine days as a covariate. The stratification factors (as randomized) will be used in the model. The least square (LS) mean treatment difference (fremanezumab - placebo), 95% confidence interval (CI) for the LS mean treatment difference, and the associated p-value will be generated from this model.

The statistical test will be two-sided at the alpha=0.05 level of significance. The SAS code for this test is as follows:

```
PROC MIXED;
  CLASS TREAT SEX REGION MIGCLASS PHQCAT;
  MODEL CHG= TREAT SEX REGION MIGCLASS PHQCAT BASE;
  LSMEANS TREAT / DIFF CL;
RUN;
```

The normality assumption for the ANCOVA model will be checked to ensure validity of the primary analysis. If the model assumptions are not met (p-value <0.01), a nonparametric method such as Wilcoxon Rank Sum test will be conducted as a sensitivity analysis.

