#### 6.2.3.2. Analysis with Multiple Imputation Method

Sensitivity analysis will be performed by imputing missing migraine days of months 1-3 using MI method. The data will be processed by the following steps.

- If a patient has partial electronic headache diary data (ie, <28 days) for a month, that month’s value will be considered missing before the MI procedure.
- For the patients in the fremanezumab treatment group who are early terminated with reasons of adverse event (AE) or lack of efficacy, they will be assigned to placebo group so their missing values will be imputed using data from the placebo treated patients.
- Run SAS PROC MI procedure to create 100 complete datasets.

The following SAS code pertains to the MI analysis:

```
PROC MI DATA=XXX SEED=SEED OUT=MI_OUT NIMPUTE=100 MAXIMUM=. . . . . 28 28
28 MINIMUM=. . . . . 0 0 0;
  CLASS TREAT SEX REGION MIGCLASS PHQCAT;
  FCS REG (AVALMI1=TREAT SEX REGION MIGCLASS PHQCAT BASE/DETAILS)
  NBITER=100;
  FCS REG (AVALMI2=TREAT SEX REGION MIGCLASS PHQCAT BASE
  AVALMI1/DETAILS) NBITER=100;
  FCS REG (AVALMI3= TREAT SEX REGION MIGCLASS PHQCAT BASE AVALMI1
  AVALMI2/DETAILS) NBITER=100;
  VAR TREAT SEX REGION MIGCLASS PHQCAT BASE AVALMI1 AVALMI2 AVALMI3;
RUN;
```

- Within each imputed data set, for a patient who has partial, say  $X$  ( $X < 28$ ) days, electronic headache diary data in a month, the monthly value will be replaced by
- $\sum(\text{observed value}) + (28 - X) * \text{imputed value} / 28$
- The monthly average number of migraine days **during the 12-week double-blind period** after the 1st dose of study drug will be the average of month 1, month 2 and month 3 values.

Each dataset will be analyzed using the same ANCOVA model as described in section 6.2.2. The LS means and SEs from each analysis will be output to a SAS data set. The SAS code for this analysis is as follows:

```
ODS OUTPUT DIFFS=MIXED_OUT;
PROC MIXED DATA=UPDATED_MI_OUT METHOD=REML;
  BY _IMPUTATION_;
  CLASS TREAT SEX REGION MIGCLASS PHQCAT;
  MODEL CHG=TREAT SEX REGION MIGCLASS PHQCAT BASE;
  LSMEANS TREAT / DIFF CL;
RUN;
```

The output dataset from the above SAS code will contain the estimate of the LS mean treatment difference and the SE of the estimate from each of the 100 datasets. SAS procedure, PROC MIANALYZE, will be used to generate an overall LS mean treatment difference, 95% CI for the LS mean treatment difference, and associated p-value. The SAS code is as follows:

```

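### The placebo-based imputation rule in SAP 6.2.3.2 is not limited to double-blind terminations, so an open-label event can change how months 1-3 are imputed, in one arm only

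*SAP*

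**What the plan says.** SAP 6.2.3.2 imputes the monthly migraine-day counts for months 1 to 3. A month with fewer than 28 diary days is first set to missing. The next step concerns a group chosen by termination reason: "For the patients in the fremanezumab treatment group who are early terminated with reasons of adverse event (AE) or lack of efficacy". These patients are placed in the placebo group so that their gaps are filled from placebo data. After imputation, a month with X observed days is rebuilt as the observed count plus (28 - X)/28 of the imputed monthly value. The ANCOVA of SAP 6.2.2 is then run on each of 100 datasets, in the ITT set.

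The step names no study period. Elsewhere, leaving early is a whole-study concept. SAP 2.1 assigns the visit 6 procedures to "Patients who withdraw from the study before completing the 24-week treatment phase", and protocol Table 4 and Appendix B label that day-169 visit as the end-of-treatment or early-termination visit. SAP 2.5.2 adds: "All analyses identified in this SAP will be performed after the final database lock". Open-label terminations and their reasons will therefore be in the data when the imputation is run.

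Where the SAP wants to separate the periods, it does so. SAP 5.2 tabulates withdrawal from double-blind treatment apart from withdrawal from the study, and SAP 8.2 distinguishes a double-blind from an open-label early withdrawal visit. The estimand in SAP 1.3 is confined to the 12-week double-blind period.

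**The concern.** The restriction to months 1-3 limits which values are imputed. It does not limit which patients are moved to placebo. A fremanezumab patient who finishes the blinded phase, takes the open-label dose at visit 5 and later stops for an adverse event or lack of efficacy satisfies the condition as written. Two things follow in the imputation step:

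- The gaps in that patient's months 1-3, all from time on blinded fremanezumab, are filled from the placebo model.
- The patient's complete fremanezumab months are used to fit the placebo model.

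A placebo-arm patient who stops after the same open-label dose for the same reason is already labelled placebo, so nothing changes. An event after the analysed period, on a dose that both arms receive, thus alters one arm only.

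Incomplete months need not be rare among completers. Month windows run from dose to dose (SAP 4.4), visits may move by 3 days either way (protocol Table 4), and about 75% diary compliance is accepted (protocol 6.1.1). A month can fall short of 28 days even with a perfect diary.

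At stake is a sensitivity analysis that should show what informative drop-out within the 12 weeks does to the result. It should not depend on what happens after week 12.

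**Working it through.** **Planning figures.** SAP 2.4 states that the trial will "provide 90% power to detect a treatment difference of 2 days with a common standard deviation of 5.2 days", with 144 evaluable patients per group. SAP 6.2.2 sets two-sided alpha at 0.05.

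- Per group: 2 × (1.960 + 1.282)² × 5.2² / 2² = 142.1, so 143 (stated 144).
- Power at 144 per group: 0.904 (stated 90%).
- Randomized: 288 / 0.85 = 338.8, so 339 (stated about 340, or 170 per group).

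The plan's figures reproduce. They supply the 170 and the 2 days used below. They do not test the wording of the rule.

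**Assumptions.** The documents do not give the number k of fremanezumab patients who stop in the open-label phase for these two reasons. I take k = 3 to 9 of 170 (about 2% to 5%), a true difference of 2 days and, for the gaps, 25% of these patients' days missing.

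**Case 1: treatment analysed as randomized.** Only the missing share of these patients' days changes, from fremanezumab-based to placebo-based values, which differ by 2 days. The shift in the arm mean is 2 × k × 0.25 / 170.

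**Case 2: placebo label kept in the ANCOVA.** Let d be the moved patients' mean benefit over placebo. Treating their months as observed, the estimated difference is (340 - k·d)/(170 - k) - k·d/(170 + k).

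- If d = 2 (average fremanezumab response), this is 2 - 2k/(170 + k).
- If d = 0 (placebo-like response), it is 2 + 2k/(170 - k).
- It equals 2 when d = 1 + k/170, which is 1.02 for k = 3 and 1.05 for k = 9. The sign therefore turns near the midpoint between the arm means.

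| k | Case 1 | Case 2, d = 2 | Case 2, d = 0 |
|---|---|---|---|
| 3 | 0.009 day, toward no difference | 0.035 day, toward no difference | 0.036 day, away from it |
| 9 | 0.026 day, toward no difference | 0.101 day, toward no difference | 0.112 day, away from it |

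**Cross-check.** The Case 1 formula leaves out the second path, in which these patients' complete months pull on the placebo model. It gives an order of magnitude and is not a bound. A simplified simulation included both paths: 300 trials per setting, 170 per arm, half of all months partial with 10% or 25% of days missing in them, and moved patients responding like their arm. It compared the literal with the limited rule on the same data:

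- As randomized, 5 moved patients: shift 0.005 and 0.011 day.
- As randomized, 10 moved patients: shift 0.008 and 0.024 day.
- Label kept: about 0.07 day for 5 patients and 0.11 day for 10.

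All these shifts are toward no difference. The simulation and the formulas agree in size.

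**The case against.** The context favours the double-blind reading. The section opens with months 1-3 and closes with the 12-week double-blind average. SAP 6.2.3.1 uses early termination for an event that leaves a month missing within the three blinded months. The two reasons match two intercurrent events of an estimand defined on those 12 weeks. SAP 2.1 speaks of withdrawing from the study and does not define the term for this analysis. I accept that double-blind termination was probably intended. Still, no sentence carries that limit into the rule, and the study-wide use of the term makes the literal reading a fair one for a programmer.

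Three stronger readings are tempting, and the documents do not support them.

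- A reader might infer that all of months 1-3 are treated as placebo data for such a patient. They are not. Complete months keep their observed values, and in a partial month only the (28 - X)/28 share is imputed. One missed day puts 1/28 of that month at issue.
- A reader might infer a bias of up to 0.1 day, always toward no difference. That size needs the placebo label to persist into the ANCOVA. SAP 6.2.3.2 has no step that restores the label, but it uses the ITT set, which SAP 3.1.1 analyses as randomized, and it gives imputation as the purpose of the reassignment. Even with the label kept, the direction is not fixed, because the rule selects patients who stopped for lack of efficacy among others.
- A reader might want placebo-based imputation confined to values after the termination date. That is a separate change. The printed PROC MI code carries one treatment value per patient across all three months, so a date condition alone would not achieve it.

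**Conclusion.** The concern holds as a selection rule without a period limit. Followed as written, SAP 6.2.3.2 lets an event after week 12 change the imputation of months 1-3 in the fremanezumab arm only, which does not fit the 12-week estimand. The primary ANCOVA, the sample size and alpha are unaffected.

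The likely effect is small: about 0.01 to 0.03 day toward no difference against a planned effect of 2 days, with treatment analysed as randomized. This rests on an assumed 3 to 9 affected patients of 170 and 25% of their days missing, neither of which the documents give. Only if the placebo label stayed in the ANCOVA could the shift reach about 0.1 day, in a direction set by how these patients responded. The case for acting is that the correction is cheap and that two programmers could now implement the step differently. The size of the bias alone would not require it.

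**What to change.** In SAP 6.2.3.2, limit the reassignment to *patients in the fremanezumab group who terminate during the double-blind treatment period (before the visit 5 dose) because of an adverse event or lack of efficacy*. Add that patients who terminate in the open-label phase keep their randomized arm when months 1-3 are imputed.

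The cost is one clause in the SAP and one condition in the program, on the termination date or on double-blind disposition, which SAP 5.2 already summarizes. No stated sample size, power or alpha changes.

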**4. Intercurrent events strategy:**

- a. Early discontinuation due to lack of efficacy: hypothetical strategy
- b. Early discontinuation due to adverse event: hypothetical strategy
- c. Initiation of prohibited therapy: hypothetical strategy
- d. Impact of COVID-19: hypothetical strategy

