### **3. ANALYSIS SETS**

#### **3.1.1. Intent-to-Treat Analysis Set**

The intent-to-treat (ITT) analysis set will include all randomized patients.

In the ITT analysis set, treatment will be assigned based on the treatment to which patients were randomized, regardless of which treatment they actually received.

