The **percentage of reduction** in the monthly average number of an efficacy variable will be calculated as

$$\frac{\text{baseline value} - \text{postbaseline value}}{\text{baseline value}} \times 100\% \quad (4)$$

where the baseline value is calculated by formula (3) and the postbaseline value in the equation is calculated by formula (1) for the variables *during the 12-week period* or by formula (2) for the variables *during the 4-week period* after each dose for months 1, 2, 3, and 6.

The mITT analysis sets will be used for all efficacy analyses. Summaries will be presented by treatment group as randomized, unless otherwise noted. For the double-blind treatment period, summaries will be presented by treatment group. For the open-label treatment period, summaries will be presented by double-blind treatment group and all patients (ie, total). Descriptive statistics for all efficacy data will be presented by month (or week), and over 12-week period for the double-blind period, and at month 6 (or week 24) for the open-label treatment period. For migraine days and PHQ-9 total score, months 1, 2, and 3 (or weeks 4, 8, and 12) will also be included in the open-label treatment period summaries.

The primary and secondary endpoints analysis listed in section 6.2.1 and section 6.3 will be repeated for the PP analysis set.

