ODS OUTPUT PARAMETERESTIMATES=PARMEST;
PROC MIANALYZE DATA=MIXED_OUT ALPHA=0-.05 THETA0=0;
  BY TREAT;
  MODELEFFECTS ESTIMATE;
  STDERR=STDERR;
RUN;
```

This sensitivity analysis will be performed on the ITT analysis set.

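### The multiple-imputation sensitivity analysis moves fremanezumab AE and lack-of-efficacy stoppers to placebo and never moves them back before the ANCOVA

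*SAP*

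**What the plan says.** SAP 6.2.3.2 sets out these steps for the multiple-imputation (MI) analysis of monthly migraine days:

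1. Months with incomplete diary data are set to missing.
2. One group of fremanezumab patients is relabelled: those who stop early for lack of efficacy or because of an adverse event (AE). The rule for this group reads: "they will be assigned to placebo group so their missing values will be imputed using data from the placebo treated patients".
3. PROC MI is run with `TREAT` in each imputation regression.
4. The put-back step, which begins "Within each imputed data set, for a patient who has partial", combines observed days with imputed values for the rest of the month.
5. The three months are averaged.
6. Each data set is analysed by "PROC MIXED DATA=UPDATED_MI_OUT METHOD=REML", with the statement "MODEL CHG=TREAT SEX REGION MIGCLASS PHQCAT BASE".

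The section closes: "This sensitivity analysis will be performed on the ITT analysis set". For that set, SAP 3.1.1 says "treatment will be assigned based on the treatment to which patients were randomized, regardless of which treatment they actually received". SAP 6.1 adds a general rule: "Summaries will be presented by treatment group as randomized, unless otherwise noted". The primary estimand (SAP 1.3) handles both kinds of stop hypothetically, for example "Early discontinuation due to lack of efficacy: hypothetical strategy".

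**The concern.** The relabelling serves imputation, but the section defines no imputation-arm variable and does not say that the arm is reset. A programmer who follows the listed steps would take the worst fremanezumab outcomes out of the fremanezumab mean and put them into the placebo mean. An analysis meant to be harsher on the drug could then look better than the primary result.

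The MMRM and the repeat ANCOVA (SAP 6.2.3.1 and 6.2.3.3) use the mITT set and apply no penalty for these stops. The MI analysis is the only primary-endpoint analysis that does, and the only efficacy analysis the SAP assigns to the ITT set.

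Two smaller points sit in the same section. The stoppers' complete on-drug months enter the imputation regression under the placebo label, although the stated aim is to use data from placebo-treated patients. And the bounds lists in PROC MI are one entry short.

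**Working it through.** **Tracing the arm variable.** `TREAT` is changed in step 2 and used in PROC MI. Steps 4 and 5 change only the outcome. PROC MIXED then reads `TREAT`. Nothing in the text or code changes it back.

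**Inputs.** SAP 2.4 gives 144 evaluable patients per arm, a 2-day difference, SD 5.2, two-sided 0.05 and 15% drop-out. Power recomputes to 0.904 (stated 90%). 288/0.85 = 338.8, so 339 (stated about 340, or 170 per arm). The MI section states no figure of its own. The share stopping for AE or lack of efficacy is not given, so I assume 2%, 5% and 10%, which is 3, 8 and 17 of 170. Unrestored, the ANCOVA arms become 167/173, 162/178 and 153/187.

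**Closed form.** Let p be the stopping share, F0 the mean change of the other fremanezumab patients, S the stoppers' mean and P the placebo mean. Negative values favour fremanezumab.

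- Arm restored: (1 − p)F0 + pS − P
- As written: F0 − (P + pS)/(1 + p)

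Set P = 0 and the restored difference to −2.0, with stoppers w days worse (S = F0 + w). Then F0 = −2 − pw.

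- 5%, w = 2: F0 = −2.10, S = −0.10; as written −2.10 + 0.005 = −2.10
- 5%, w = 4: F0 = −2.20, S = 1.80; as written −2.20 − 0.05 × 1.80/1.05 = −2.29
- 10%, w = 2: F0 = −2.20, S = −0.20; as written −2.20 + 0.018 = −2.18
- 10%, w = 0: F0 = S = −2.00; as written −2.00 + 0.10 × 2.00/1.10 = −1.82

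As written beats restored when S > [F0(1 + p) + P]/(2 + p). With p = 0.05, F0 = −2 and P = 0, this is −2.10/2.05 = −1.02, so the break-even is stoppers about 1 day worse than F0.

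**Simulation.** The set-up was 170 per arm, 400 trials per scenario and 5 imputations. The arm difference was 2.0 days before truncation to 0–28 (about 1.75 after), baseline mean 14 (SD 5.5) and SD of change about 4.8. Stopping was equal in both arms, half after month 1 and half after month 2. Imputation was sequential regression on arm, baseline and earlier months. The primary estimate used the average of the observed months. Draws differ between rows, so compare within rows.

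| Stoppers | Days worse | Primary | MI, arm restored | MI as written |
|---|---|---|---|---|
| 2% | 2 | −1.75 | −1.74 | −1.77 |
| 2% | 4 | −1.78 | −1.77 | −1.86 |
| 5% | 0 | −1.78 | −1.76 | −1.72 |
| 5% | 2 | −1.80 | −1.78 | −1.88 |
| 5% | 4 | −1.79 | −1.78 | −2.00 |
| 10% | 2 | −1.72 | −1.69 | −1.88 |
| 10% | 4 | −1.74 | −1.71 | −2.17 |

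The Monte Carlo standard error of as written minus primary is 0.005 to 0.012. A separate simulation gave the same pattern: −1.76/−1.74/−1.98 (5%, 4 days), −1.82/−1.79/−2.25 (10%, 4 days) and −1.78/−1.77/−1.72 (5%, 0 days).

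**Smaller points.** Excluding the stoppers' own months from the regression moved the estimate by at most 0.004 day. `MAXIMUM` and `MINIMUM` each have 5 placeholders and 3 limits, 8 entries in all, against 9 variables in `VAR`. Read by position, the 0–28 limits fall on `BASE`, `AVALMI1` and `AVALMI2`, and `AVALMI3` is unbounded. That moved the estimate by at most 0.006 day (restored) or 0.012 day (as written).

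**The case against.** The best reply is that restoration is plainly intended. The relabelling is tied to a purpose, the section calls for the same ANCOVA as in SAP 6.2.2, and the ITT set is as randomized. The code is a template: `UPDATED_MI_OUT` must come from a data step that is not printed, which could also reset the arm. This is probably right about intent, and I do not suggest the sponsor means to analyse these patients as placebo. But the processing steps are listed and the arm is not among them. A prespecified analysis should not depend on an unstated correction.

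Two supporting texts are weaker than SAP 3.1.1. The rule in SAP 6.1 allows exceptions, and the closing line of 6.2.3.2 only names the analysis set. The conflict rests on SAP 3.1.1.

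The size can also be challenged. The 15% drop-out covers all reasons over the whole study, so 10% would be two-thirds of it. Protocol 1.2.2.2 describes AE discontinuations in both pivotal trials as infrequent. The 2% and 5% rows are therefore the more plausible ones. Correctly run, the analysis differs from the primary by only 0.01 to 0.03 day, so the penalty lost is small. What matters more is the bias when stoppers do clearly worse.

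Finally, migraine-day results have another safeguard: the responder endpoint, inside the hierarchy, counts early discontinuers as non-responders (SAP 6.3.2.1). Protocol 9.5.4.2 says only that MI may be conducted, although Protocol 9.3 says it will be. The bounds point is trivial in size, and a placeholder may have been lost in text extraction, so it should be checked against the source file.

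**Conclusion.** The concern holds. As written, SAP 6.2.3.2 analyses fremanezumab AE and lack-of-efficacy stoppers as placebo patients, on a set that SAP 3.1.1 defines by randomization.

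With stoppers 2 to 4 days worse, the as-written estimate exceeds the primary by 0.02 to 0.08 day at 2% stopping, 0.08 to 0.21 at 5% and 0.16 to 0.43 at 10%. If stoppers do no worse than other fremanezumab patients, it falls short of the primary (by 0.06 day at 5%). These sizes rest on assumed stopping shares and outcomes.

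The primary analysis, its p-value, the testing hierarchy and the sample size are untouched. The risk is a robustness check that falsely reassures. It should be corrected, but it does not threaten the trial's main conclusion. The regression-label and bounds points are tidying.

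**What to change.** - Keep the randomized arm in `TREAT` throughout, and define a separate variable for the imputation arm.
- State that the ANCOVA on the imputed data uses randomized `TREAT`.
- Fit the placebo imputation regression on placebo-randomized patients only, and apply it to the fremanezumab AE and lack-of-efficacy stoppers.
- Add a sixth placeholder to both bounds lists, so that 0–28 falls on `AVALMI1` to `AVALMI3`.
- Leave the partial-month rule alone. The put-back step keeps the observed days, and imputing the rest is how this analysis tests proration.

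The cost is SAP text and code edits only. Data collection, sample size and conduct do not change. The sensitivity estimate may become slightly less favourable.

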### 4.4. Study Days and Visits

Study days are numbered relative to the 1st day of study drug administration. The start of treatment (day 1) is defined as the date on which a patient takes the 1st dose of study drug, as recorded on the study drug administration case report form (CRF). Days will be numbered relative to treatment start (ie, ..., -2, -1, 1, 2, ...; with day 1 being the 1st day of study drug administration and day -1 being the day before the 1st day of study drug administration).

The 4-week (28-day) visit windows for the electronic headache diary based efficacy endpoints will be determined based on the actual dosing day. The run-in phase is defined as day -28 to -1 before the 1st injection on day 1. Treatment phase including month 1, 2, 3, and 6 is from the beginning of the 1st injection of study drug to visit 6/day 169 or the EOT visit. The monthly visit windows are separated by each dosing date/time. Month 1 is from the date/time of the 1st dose of study drug administration on day 1 to the date/time just before the 2nd dose. Month 2 is from the date/time of the 2nd dose to the date/time just before the 3rd dose. Month 3 is from the date/time of the 3rd dose to the date/time just before the 4th dose. Month 6 is from 57 days after the date/time of the 4th dose to the EOT on day 169 approximately.

Throughout this document, all by month efficacy summaries for the headache data will refer to these visit windows.

For all other by-visit summaries, if there are multiple assessments at a postbaseline visit then the last non-missing assessment at that visit will be used for the summary. This includes assessments at the scheduled and unscheduled visits.

For patients who withdraw from the study, their efficacy and safety data at the early termination visit will be excluded from the by-visit summaries but will be included in the last assessment summaries.

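### The multiple-imputation code ignores known later months, which makes its standard error slightly too small when diary gaps are intermittent, and its limit lists are one entry short

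*SAP*

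**What the plan says.** SAP 6.2.3.2 gives the imputation step as SAS code with one regression model per month.

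- Month 1 has no other month as predictor: "FCS REG (AVALMI1=TREAT SEX REGION MIGCLASS PHQCAT BASE/DETAILS".
- Month 2 begins "FCS REG (AVALMI2=TREAT SEX REGION MIGCLASS PHQCAT BASE" and adds only AVALMI1 on the next line.
- Month 3 begins "FCS REG (AVALMI3= TREAT SEX REGION MIGCLASS PHQCAT BASE AVALMI1" and also takes AVALMI2.

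Before imputation, if a month holds fewer than 28 days of diary data, its "value will be considered missing before the MI procedure". Afterwards the observed days are put back: where a patient has X days of "electronic headache diary data in a month, the monthly value will be replaced by" the observed total plus (28 - X)/28 of the imputed value.

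The limits are set by "NIMPUTE=100 MAXIMUM=. . . . . 28 28" with a third 28 on the following line, and MINIMUM has five dots and three zeros. The variable list is "VAR TREAT SEX REGION MIGCLASS PHQCAT BASE AVALMI1 AVALMI2 AVALMI3".

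The analysis runs on the ITT set. The primary ANCOVA (6.2.2) and the MMRM sensitivity analysis (6.2.3.1) use the mITT set.

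**The concern.** A chain in which only earlier months predict later ones loses nothing if a patient who misses one month also misses all later ones. The plan's own rules produce a different pattern.

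- Protocol 6.1.1 asks for about 75% diary compliance and closes entry for a day after 48 hours.
- SAP 4.4 cuts months at doses ("The monthly visit windows are separated by each dosing date/time"), and Protocol Table 4 allows visits 3 to 5 a window of ±3 days. A month can therefore fall short of 28 days even with a full diary.

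A patient may thus have month 1 blanked while months 2 and 3 are known. The code then draws month 1 as if it were unrelated to them. The completed months are too weakly correlated within the patient, the three-month average varies too little between patients, and the standard error is too small.

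This is the only analysis of the primary endpoint that SAP 6.2 places on the full ITT set, and the only one that imputes adverse-event and lack-of-efficacy dropouts from placebo data. Such a check should not report more precision than the data support.

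**Working it through.** **The plan's own figure.** The documents give no standard error for this analysis. The nearest stated figure is the power (SAP 2.4): 144 per arm, difference 2, SD 5.2, two-sided 0.05. The standard error is 5.2 × √(2/144) = 0.613, and 2/0.613 - 1.96 = 1.30, so power is 0.904. The stated 90% is reproduced. For dropout, 288/0.85 = 339, which agrees with about 340 randomized.

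**Counting the limits.** VAR has nine names. MAXIMUM has 5 + 3 = 8 entries, and so has MINIMUM. By position, entries 1 to 5 (dots) go to TREAT, SEX, REGION, MIGCLASS and PHQCAT. Entries 6, 7 and 8 (0 to 28) go to BASE, AVALMI1 and AVALMI2. Entry 9, AVALMI3, has nothing.

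**How common are blanked months?** The documents give no rate. If daily entries were independent (an assumption), 98% daily entry leaves 0.98^28 = 57% of months complete, and 95% leaves 0.95^28 = 24%.

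**Closed form.** Suppose month 1 is wholly missing at random in a share m of patients and months 2 and 3 are complete. Let the residual variance be σ², the between-month correlation ρ, and n the number per arm. In units of σ²/(9n), for one arm's mean of the three-month average:

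- true variance = 3 + 6ρ + m/(1 - m)
- Rubin variance from the chain = 3 + 6ρ + m/(1 - m) - 4ρm

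The last term is the lost covariance of month 1 with months 2 and 3. With ρ = 0.7:

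- m = 10%: 7.311 against 7.031, so the SE is √(7.031/7.311) = 0.981 of the true SE.
- m = 30%: 7.629 against 6.789, so the SE is 0.943 of the true SE.

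Both Rubin variances are below the complete-data value of 7.2. At ρ = 0.5 the ratios are 0.984 and 0.952; at ρ = 0.8 they are 0.980 and 0.940.

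**Simulation of the SAP steps** (chain, weighting by missing days, ANCOVA, Rubin's rules): 170 per arm, 600 trials, 20 imputations. Three settings are assumptions, not taken from the documents: mean baseline 14 days, ρ of 0.5 or 0.8, and gaps completely at random. No limits were applied in the table. The mean complete-data SE is 0.514 (ρ = 0.5) and 0.526 (ρ = 0.8).

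| Gap pattern | ρ | SE as coded | SE, all months as predictors | Reduction |
|---|---|---|---|---|
| Dropout only, 15% | 0.5 | 0.525 | 0.525 | none |
| | 0.8 | 0.535 | 0.534 | none |
| Whole months, 10%, intermittent | 0.5 | 0.516 | 0.525 | 1.7% |
| | 0.8 | 0.522 | 0.530 | 1.5% |
| Half of months partial, 21-27 days | 0.5 | 0.489 | 0.499 | 2.0% |
| | 0.8 | 0.502 | 0.517 | 2.9% |
| Half of months partial, 10-27 days | 0.5 | 0.479 | 0.500 | 4.2% |
| | 0.8 | 0.486 | 0.515 | 5.6% |
| 15% dropout + half partial, 21-27 days | 0.5 | 0.498 | 0.513 | 2.9% |
| | 0.8 | 0.507 | 0.526 | 3.6% |
| 15% dropout + 80% partial, 24-27 days | 0.5 | 0.504 | 0.514 | 1.9% |
| | 0.8 | 0.506 | 0.518 | 2.3% |

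In every partial-month row the SE as coded is below the complete-data SE. The treatment estimates of the two methods differ by at most 0.007 day.

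Over the intermittent patterns, the SE as coded is 0.90 to 0.97 of the empirical SD. With all months as predictors it is 0.91 to 0.99, and with complete data 0.98 to 0.99. With 600 trials each empirical SD is itself uncertain by about 1/√1200 = 2.9%.

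**Limits in the simulation.** With months 1 and 2 limited and month 3 not, 5% to 10% of imputed month 3 values fall outside 0 to 28. Limiting month 3 as well moves the treatment estimate by at most 0.025 day.

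**The case against.** The strongest reply is that this hardly matters. The largest gap in the table (0.486 against 0.515) changes the half-width of a 95% interval by 1.96 × 0.029 = 0.057 day. At the planned 2-day effect, 2/0.515 = 3.9 and 2/0.486 = 4.1 lead to the same conclusion. The primary ANCOVA does not use this code, and the MMRM models the three months jointly with an unstructured covariance. This stands, and it keeps the point minor. It can also be said that Protocol 9.5.4.2 makes multiple imputation optional, but Protocol 9.3 and SAP 6.2.3.2 commit to it.

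Some stronger inferences are not supported:

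- **The standard errors are too small whatever the gaps.** Under dropout alone the chain costs nothing, and two of the intercurrent events in the SAP's estimand section are early discontinuations.
- **Month 3 is certainly unbounded, so negative migraine days enter the analysis.** The documents do not say how a short list is treated; it could stop the run. Under the positional reading, a month with 21 diary days gives its imputed value only 7/28 = 25% weight, and the ANCOVA then averages three months. A separate check assumed baseline mean 13, residual SD 4.5, ρ 0.5 to 0.8, 95-98% daily entry and 15% dropout. It found about 7% of raw month 3 imputations negative, but only 0.3% to 0.6% of three-month averages.
- **Limits distort the means, so predictive mean matching is required.** The size of any distortion rests on assumed means and SDs, and the argument sits badly with faulting month 3 for having no limits. Matching is a reasonable preference, not the correction of an error.

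**Conclusion.** Wrong as written, and minor, because only a sensitivity analysis is affected. Both coding facts can be read directly from SAP 6.2.3.2, and that section's 28-day rule ensures the gap pattern that the chain does not suit.

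The standard error is about 1.5% to 6% too small. That range rests on between-month correlations of 0.5 to 0.8, gaps completely at random, and assumed rates of blanked months; the documents give none of these. With dropout only, the effect is nil. The treatment estimate is essentially unchanged.

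The limit lists do not do what three 0-28 pairs intend, whether they are read by position or rejected.

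A reader might infer that adding the missing predictors makes the intervals fully correct. That holds for wholly missing months, where the SE returns to 0.98-0.99 of the empirical SD. It does not hold for partial months, where the ratio stays at about 0.91 to 0.97. There the imputation ignores the days that the patient did record in that month, which is a separate weakness.

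**What to change.** In the FCS specification, predict each of AVALMI1, AVALMI2 and AVALMI3 from TREAT, SEX, REGION, MIGCLASS, PHQCAT, BASE and both other months. In MAXIMUM and MINIMUM, put six placeholders before the three limits, so that each list has nine entries in VAR order. Predictive mean matching without limits is an optional alternative.

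State in the SAP that some understatement remains for partial months, because their observed days do not inform the imputed value.

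The cost is a few lines of code. It needs no new data and changes neither the estimand nor the primary analysis. Make the change while the study is still blinded, so that it does not surface later as an unplanned programming deviation.
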